### **11.3 Monitoring of AEs and Period of Observation**

AEs, both nonserious and serious, will be monitored throughout the study as follows:

- AEs will be reported from the first dose of study drug through 30 days after administration of the last dose of study drug and recorded in the eCRFs.
- Serious PTEs will be reported to the Takeda Global Pharmacovigilance department or designee from the time of the signing of the ICF up to the first dose of study drug, but will not be recorded in the eCRF.
- Related and unrelated SAEs will be reported to the Takeda Global Pharmacovigilance department or designee from the first dose of study drug through 30 days after administration of the last dose of study drug and recorded in the eCRF. After this period, only related SAEs must be reported to the Takeda Global Pharmacovigilance department or designee. SAEs should be monitored until they are resolved or are clearly determined to be due to a patient's stable or chronic condition or intercurrent illness(es).

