**Table 7.a Imputation Rules for Missing AE Start Dates**

Non- missing	Missing	Estimated
Month and Year	Day	Day of first dose date of STUDY DRUG, if month and year of onset date are the same as month and year of date of first dose.  The last day of the month, if the month and year of onset date are before the month and year of date of first dose of STUDY DRUG.  The first day of the month, if the month and year of onset date are after the month and year of date of first dose of STUDY DRUG.
Year	Day and Month	Day and month of first dose date of STUDY DRUG, if the year of onset date is the same as the year of date of first dose of STUDY DRUG.  December 31st, if the year of onset date is prior to the year of date of first dose of STUDY DRUG.  January 1st, if the year of onset date is after the year of date of first dose of STUDY DRUG.
Day, Month and Year		Date of first dose of STUDY DRUG

Missing or partial AE stop dates will be imputed according to the following rules. If only the day is missing, use 15th of the month; if both month and day are missing, use June 30th. For a record with a complete start date and a partial stop date, if the estimated stop date would become earlier than the start date, the stop date will not be estimated.

If AE stop date is not missing and AE stop date < estimated start date, let estimated onset date = AE stop date.

All dates presented in listings are recorded dates without imputation.

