### 7.1.4 Conventions for Missing Concomitant Medication Dates

If only the day is missing, use 15th of the month; if both month and day are missing, use June 30th. For a record with a complete start date and a partial stop date, if the imputed stop date would become earlier than the start date, the stop date will not be estimated.

All dates presented in listings are recorded dates without imputation.

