#### *7.11.1.2 Peripheral Neuropathies*

Peripheral Neuropathy (PN) is defined by the peripheral neuropathy SMQ broad search. The incidence of treatment-emergent PN and treatment-emergent drug-related PN will each be summarized by preferred term and severity. The incidence of peripheral motor neuropathy will also be calculated. Time to onset, resolution and improvement of PN events will be summarized. Individual plot by preferred term for treatment-emergent peripheral neuropathy (SMQ) may be presented.

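### Partial stop dates set to the 15th or 30 June can blank an AE's end date, conflict with its imputed onset, or end a concomitant medication before the first dose

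*SAP*

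**What the plan says.** SAP 7.1.3 announces that "Missing or partial AE stop dates will be imputed according to the following rules" and then gives the values: "If only the day is missing, use 15th of the month; if both month and day are missing, use June 30th". A guard follows. Its scope is "For a record with a complete start date and a partial stop date", and its effect is that "if the estimated stop date would become earlier than the start date, the stop date will not be estimated". A separate reset rule reads: "If AE stop date is not missing and AE stop date < estimated start date, let estimated onset date = AE stop date". Listings show the dates as recorded.

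For start dates, Table 7.a uses the first dose date when the known month and year, or the known year alone, match those of first dose.

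SAP 7.1.4 gives medications the same 15th and 30 June values and the same guard ("if the imputed stop date would become earlier than the start date, the stop date will not be estimated"), with no reset rule. SAP 7.6 counts a medication as concomitant if it was given between first dose and the end-of-treatment visit.

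The dates are used in two places. SAP 7.11.1 defines treatment-emergent AEs (TEAEs) as those occurring after first dose and up to 30 days after the last dose. SAP 7.11.1.2 states: "Time to onset, resolution and improvement of PN events will be summarized". On collection, Protocol 11.3 states: "AEs will be reported from the first dose of study drug through 30 days after administration of the last dose of study drug". Protocol 10.3.12 records medications from first dose.

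**The concern.** A mid-period value is a usual convention for a partial date, but it needs protection where it conflicts with something known. Here the protection is incomplete in three ways.

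- When the value conflicts with a complete start, the guard discards it and leaves no end date. The event is still known to have ended in a stated month or year. The records affected are short events that begin late in the period.
- When the start is also partial, the guard does not apply. Table 7.a assigns a doubtful onset to the first dose date, and the stop rule can contradict that.
- For medications, an imputed stop alone can place before first dose a drug that was recorded because it was used from first dose onward.

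The analyses at stake are time to resolution of peripheral neuropathy and, under one reading, TEAE status. AEs are part of the primary safety endpoint. With about 30 patients, a few records are visible. If the 44% sensory neuropathy rate in Protocol 4.1.4 applied here, 0.44 × 30 ≈ 13 patients would be affected by neuropathy, and one missing resolution date would be 1/13 ≈ 8% of them.

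**Working it through.** The plan gives no figure to reproduce, so the check applies the printed rules to illustrative dates.

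**(a) Complete start, partial stop.** Start 20 May, stop recorded only as May. The stop rule gives 15 May, which is before 20 May, so the guard leaves the stop blank. The event ended between 20 and 31 May, at most 11 days after it began, but has no analysis end date.

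**(b) Both dates partial, in the month or year of first dose.** First dose 20 June, start and stop both recorded only as June. Table 7.a gives start 20 June; the stop rule gives 15 June. The guard is limited to complete starts. What follows depends on whether an imputed stop counts as not missing in the reset rule.

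| Reading | Onset | Stop | Result |
|---|---|---|---|
| A: only a recorded stop counts | 20 June | 15 June | ends 5 days before it starts |
| B: an imputed stop also counts | 15 June | 15 June | onset 5 days before first dose; not a TEAE |

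With first dose 20 August 2018 and both dates recorded only as 2018, reading A gives 20 August to 30 June. Reading B gives onset 30 June, which is 51 days before first dose.

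**(c) Medications.** First dose 20 June, stop recorded only as June: the stop becomes 15 June. If the start is complete and falls on or before 15 June, the guard is not triggered, and the medication ends before first dose and leaves the SAP 7.6 definition. If a complete start falls after 15 June, the guard blanks the stop and the medication stays in.

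**Exposure.** In a 365-day year, 185 days fall after the 15th of their month (185/365 = 50.7%) and 184 fall after 30 June (184/365 = 50.4%). For (a), among 2018 start dates whose stop falls in the same month (or year), the share starting after the imputed stop depends on duration:

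| Stop missing | Duration (days) and share starting too late |
|---|---|
| Day only | 0: 50.7%; 5: 41.0%; 10: 26.5%; 14: 9.1%; 20: 0% |
| Day and month | 0: 50.4%; 60: 40.7%; 120: 26.1%; 180: 2.2% |

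**Illustrative grid.** Assumptions: first dose on every second day of 2018, onset 0 to 387 days later in steps of 3, duration 0 to 120 days in steps of 4. That is 183 × 130 × 31 = 737,490 events for each combination of date completeness.

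| Start | Stop | Result under the SAP rules |
|---|---|---|
| Complete | Day missing | 4.0% blank stop |
| Complete | Year only | 34.0% blank stop |
| Day missing | Day missing | about 0.1%: A end before start, B pre-dose onset |
| Day missing | Year only | A 34.0% end before start; B 5.9% pre-dose onset |
| Year only | Year only | 5.9%: A end before start, B pre-dose onset |

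Reading A never gave a pre-dose onset, and reading B never gave an end before a start. These percentages describe the assumed grid, not rates expected in the trial.

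**The case against.** The midpoint is a legitimate convention, and most partial dates will cause no conflict. When only the day is missing, the loss in (a) needs onset and resolution in the same month, and Protocol 4.1.5 describes this neuropathy as typically cumulative. Protocol 9.6.4 and 10.3.13 ask for close follow-up of neuropathy, and the logic checks in Protocol 13.1 look for missing and inconsistent dates, so partial dates may be few. All of this stands and limits the size of the point. It does not supply a rule for the partial dates that remain.

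A reader might infer that about half of such events lose their end date. That holds only at near-zero duration.

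A reader might also infer that the rules produce both negative durations and pre-dose onsets. For AEs these are alternatives. The wording supports either reading: the SAP names missing and partial stops as separate cases, which favours B, but it calls an imputed stop estimated in the guard and drops that word in the reset rule, which favours A. Under A, TEAE status never changes. TEAE incidence does not otherwise use stop dates, so damage to the primary safety endpoint is conditional.

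Nor do the documents show that time to resolution is biased in a known direction. The SAP does not say how an event with a blank stop is analysed, or whether a recorded outcome would still count it as resolved. The listings keep what was recorded.

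**Conclusion.** The point holds as a minor defect. Applied literally, SAP 7.1.3 drops the analysis end date of some short events whose month or year of resolution is known. It also leaves a conflict between imputed start and imputed stop around first dose, with two possible outcomes and no statement of which is meant; two programmers could assign different TEAE status to one record. SAP 7.1.4 can remove a medication from the concomitant table on the strength of an imputed stop alone. Exposure is at most about half of calendar dates, and the share affected falls to zero by 20 days' duration when only the day is missing. Year-only stops are the more vulnerable case. The actual effect cannot be sized, because the documents do not say how many dates will be partial.

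**What to change.** In SAP 7.1.3:

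- Never let an imputed stop precede the recorded or imputed start; this extends the guard to partial starts.
- Where the 15th or 30 June would do so, use the last day of the known month (31 December if the month is missing), capped at death, last contact or data cut-off, instead of a blank.
- Apply the reset of onset to the stop date only when the stop is fully recorded.
- If even the last day of the known period precedes the start, the recorded information itself conflicts, and the record should be queried.

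In SAP 7.1.4, use the same rule, and do not let an imputed stop alone place before first dose a medication recorded from first dose onward.

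Run on the grid above, the AE rules give no blank stops, no end before a start and no pre-dose onsets.

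The cost is a few SAP sentences and a small programming change before database lock, with no effect on conduct. The affected events get a later imputed stop: up to about half a month (31 − 15 = 16 days), or up to 184 days for year-only stops (30 June to 31 December) before the cap. Using the last day for all partial stops is simpler and also acceptable, but it lengthens every partially dated event, including those with no conflict. SAP 7.6 already uses the last day for prior therapies, though only to put them in order, so it is a limited precedent.

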### 7.1.4 Conventions for Missing Concomitant Medication Dates

If only the day is missing, use 15th of the month; if both month and day are missing, use June 30th. For a record with a complete start date and a partial stop date, if the imputed stop date would become earlier than the start date, the stop date will not be estimated.

All dates presented in listings are recorded dates without imputation.

## 7.2 Analysis Sets

### 7.2.1 Safety/Modified Intent-to-Treat Population

The safety/modified intent-to-treat (mITT) population consists of all subjects who have measurable lesions at Baseline and receive at least 1 dose of brentuximab vedotin. The safety/mITT population will be used for analyses of efficacy, safety, and patient demographics and baseline disease characteristics, unless otherwise stated.

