## **8.0 STUDY POPULATION**

### **8.1 Inclusion Criteria**

Each patient must meet all of the following inclusion criteria to be enrolled in the study:

1. Male or female Chinese patients aged 18 years or older at the time of informed consent.
2. Patients must have histologically confirmed CD30+ HL or sALCL. Immunohistochemistry or flow cytometry may be performed on either original diagnostic biopsy material or biopsy of relapsed disease, and pathology reports of CD30+ or their copies should be retained at the site.
3. Patients with CD30+ HL or sALCL who have relapsed from or are refractory to previous treatments.
4. Fluorodeoxyglucose (FDG)-PET positive and measurable disease of at least 1.5 cm in the longest diameter by CT, as assessed by the site.
5. Patients must have an Eastern Cooperative Oncology Group (ECOG) performance status of 0 or 1.
6. Voluntary written consent must be given before performance of any study-related procedure not part of standard medical care, with the understanding that consent may be withdrawn by the patient at any time without prejudice to future medical care.
7. Female patients who:
  - Are postmenopausal for at least 1 year before the screening visit, OR
  - Are surgically sterile, OR
  - If they are of childbearing potential, agree to practice 2 effective methods of contraception, at the same time, from the time of signing the informed consent through 6 months after the last dose of study drug.

Male patients, even if surgically sterilized (ie, status postvasectomy), who:

- Agree to practice effective barrier contraception during the entire study treatment period and through 6 months after the last dose of study drug.

8. Suitable venous access for the study-required blood sampling, including PK sampling.
9. Patients must have the following required screening laboratory data. Patients must not have received recombinant granulocyte-colony stimulating factor (G-CSF) or platelet transfusion within 1 week before the screening hematology assessment.
  - Absolute neutrophil count  $\geq 1500/\mu\text{L}$ .
  - Platelet count  $\geq 75,000/\mu\text{L}$ .
  - Serum bilirubin level  $\leq 1.5$  times the upper limit of the normal range (ULN).
  - Serum creatinine level  $\leq 1.5$  times the ULN.

- Alanine aminotransferase (ALT) and aspartate aminotransferase (AST)  $\leq 2.5$  times the ULN.
- 10. Survival for 3 or more months must be expected.

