## **10.6 Discontinuation of Treatment With Study Drug and Patient Replacement**

Treatment with study drug may be discontinued for any of the following reasons:

- AE.
- Protocol violation.
- PD.
- Study terminated by sponsor.
- Withdrawal by subject.
- Lost to follow-up.
- Administrative decision by the investigator/subinvestigator or the sponsor.
- Pregnancy.
- Completed 16 cycles of treatment at response (CR or PR) or SD.
- Initiation of subsequent stem cell transplant
- Other.

Once study drug has been discontinued, all study procedures outlined for the safety follow-up visit will be completed as specified in the Schedule of Events ([Appendix A](#)). The primary reason for study drug discontinuation will be recorded on the eCRF.

Reasons that may cause a subject to be replaced include but are not limited to:

- Patient does not meet Inclusion Criterion 2.
- Patient has not taken at least 1 dose of brentuximab vedotin.
- Patient is not response evaluable according to the Revised Response Criteria for Malignant Lymphoma [1].

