#### **14.1.7 Safety Analysis**

Safety will be evaluated by the incidence of AEs, severity and type of AEs, and by changes from Baseline in the patient's vital signs and clinical laboratory results using the safety population. Exposure to study drug, including the number of treated cycles, total amount of doses taken, and dose intensity will be summarized.

TEAEs that occur after administration of the first dose of study drug and through 30 days after the last dose of study drug will be tabulated. A listing of deaths and TEAEs resulting in study drug discontinuation will be provided.

AEs will be tabulated according to the MedDRA and will include the following categories:

- TEAEs.
- Drug-related TEAEs.
- Grade 3 or higher TEAEs.
- Grade 3 or higher drug-related TEAEs.
- SAEs.

Descriptive statistics for the actual values of clinical laboratory parameters (and/or change from Baseline in clinical laboratory parameters) will be presented for all scheduled measurements over time. Mean laboratory values over time will be plotted for key laboratory parameters. Shift tables for laboratory parameters will be generated based on changes in NCI CTCAE grade from Baseline to the worst post-Baseline value. Graphical displays of key safety parameters, such as scatter plots of Baseline versus worst post-Baseline values, may be used to understand the brentuximab vedotin safety profile.

Descriptive statistics for the actual values (and/or the changes from Baseline) of vital signs (eg, blood pressure, pulse rate, and axillary temperatures) and weight over time will be tabulated by scheduled time point. ECOG performance status scores over time will also be tabulated.

Additional safety analyses may be performed to most clearly enumerate rates of toxicities and to further define the safety profile of brentuximab vedotin.

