### **15.2 Protocol Deviations**

The investigator should not deviate from the protocol, except where necessary to eliminate an immediate hazard to study subjects. Should other unexpected circumstances arise that will require deviation from protocol-specified procedures, the investigator should consult with the sponsor or designee (and IRB or IEC, as required) to determine the appropriate course of action. There will be no exemptions (a prospectively approved deviation) from the inclusion or exclusion criteria.

The site should document all protocol deviations in the subject's source documents. In the event of a significant deviation, the site should notify the sponsor or its designee (and IRB or IEC, as required). Significant deviations include, but are not limited to, those that involve fraud or misconduct, increase the health risk to the subject, or confound interpretation of primary study assessment. A Protocol Deviation Form should be completed by the site and signed by the sponsor or designee for any significant deviation from the protocol.

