## 7.0 METHODS OF ANALYSIS AND PRESENTATION

### 7.1 General Principles

In general, descriptive statistics (number of observations, mean, standard deviation [StdDev], median, minimum, and maximum) will be used to summarize continuous variables. Frequency and percentage will be used to summarize categorical variables. Time-to-event data will be analyzed using the Kaplan-Meier method and results will be summarized by the 25th, 50th (median), and 75th percentiles, if estimable, with associated 2-sided 95% confidence intervals, as well as the percentage of censored observations.

Means and medians will be presented to 1 more decimal place than the recorded data. The standard deviations (StdDev) will be presented to 2 more decimal places than the recorded data. Confidence intervals about a parameter estimate will be presented using the same number of decimal places as the parameter estimate.

Unless otherwise specified, safety and efficacy data will be summarized in the following 3 groups: patients with r/r HL only, patients with r/r sALCL only, all patients. Analyses pertaining to pharmacokinetics and immunogenicity will be summarized by treatment cycle at the prespecified time points.

The baseline value is defined as the value collected at the time closest to, but prior to, the start of study drug administration, unless otherwise specified. A windowing convention may be used to determine the analysis value for a given study visit for observed data analyses.

All available efficacy and safety data will be included in data listings and tabulations. Data that are potentially spurious or erroneous will be examined under the auspices of standard data management operating procedures. In general, there will be no imputation of missing data. For time-related endpoints, subjects who have no specified events will be censored as specified for each respective endpoint in Section 7.8. Imputation rules for missing dates of AEs and concomitant medications are detailed in Sections 7.1.3 and 7.1.4.

The primary analysis for the clinical study report including the primary and the secondary endpoints will be conducted when all patients have had the opportunity to receive 16 cycles of treatment and have had EOT assessments. The results will be summarized in the primary CSR. The final analysis will be conducted when all patients have had the opportunity to be followed for 18 months after EOT. These results will be summarized in the CSR Addendum.

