### 7.3.1 Protocol Deviations

Protocol deviation will be collected by clinical team and entered into clinical trial management system (CTMS). Important protocol deviation criteria will be established as “Major” in Protocol Deviation and patients with important protocol deviations will be identified and documented before database lock. Important protocol deviations and the number of subjects with important protocol deviations will be tabulated for enrolled patients with HL, with sALCL, and for the combined populations.

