## 7.11 Safety Analysis

Safety will be evaluated by the incidence of treatment-emergent AEs (TEAEs), severity and type of AEs, and by changes from baseline in the patient's vital signs, neurotoxicity assessment, ECGs, and clinical laboratory results. Exposure to study drug and reasons for discontinuation will also be tabulated.

These analyses will be performed using the safety/mITT population.

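### The only safety analysis set requires a measurable baseline lesion as well as a dose, so a treated patient without one would drop out of the safety incidence tables

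*SAP*

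**What the plan says.** Protocol 14.1.1 and SAP 7.2.1 define the combined safety/mITT population in the same words: it "consists of all subjects who have measurable lesions at Baseline and receive at least 1 dose of brentuximab vedotin". Both conditions must be met.

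For the safety tables, SAP 7.11 says: "These analyses will be performed using the safety/mITT population". Protocol 14.1.7 describes changes from Baseline in "vital signs and clinical laboratory results using the safety population", but no separate safety population is defined. The other sets are per-protocol, PK and, in the SAP only, Immunogenicity. None of them is a set of all treated patients, and SAP 7.13 adds none.

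Other text bears on the point:

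- SAP 7.1 states: "All available efficacy and safety data will be included in data listings and tabulations".
- Protocol 8.1, criterion 4, requires FDG-PET-positive disease and "measurable disease of at least 1.5 cm in the longest diameter by CT, as assessed by the site".
- Protocol 15.2 states: "There will be no exemptions (a prospectively approved deviation) from the inclusion or exclusion criteria".
- Protocol 10.6 lists reasons for which a patient may be replaced, among them "Patient is not response evaluable according to the Revised Response Criteria for Malignant Lymphoma".
- SAP 7.3.1 says that important deviations "will be tabulated for enrolled patients with HL, with sALCL, and for the combined populations".

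**The concern.** Safety is a primary endpoint in both documents (Protocol 6.1, SAP 5.1). Its incidence tables should count everyone exposed to the drug. A baseline tumor measurement decides whether response can be assessed, which is a reason to restrict an efficacy set. Merging the two sets carries that restriction into the safety denominator.

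As written, a patient who is dosed and then found to have no measurable lesion is left out of the AE, laboratory, vital sign, ECG and exposure tables. The same patient could still be counted elsewhere:

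- The deviation table covers enrolled patients, so it would count the eligibility error if that is classed as important.
- The Immunogenicity population (SAP 7.2.4) needs a dose and ATA samples but no lesion, and SAP 7.10.1 allows AE incidence to be tabulated by ATA status.

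Disposition percentages (SAP 7.3) also use safety/mITT as denominator, and no category there shows the number treated, so the omission might not be noticed.

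**Working it through.** **The plan's own figures.** The stated probabilities of success reproduce. P(X ≥ 9 | n = 22, p = 0.65) = 0.9942, against a stated value above 99%. P(X ≥ 5 | n = 8, p = 0.80) = 0.9437, against a stated value above 94%. The exact 95% CIs also match: 20.7% to 63.6% for 9/22 and 24.5% to 91.5% for 5/8. They concern response, and the point here does not depend on them.

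**Inputs.** The planned numbers are about 22 HL, 8 sALCL and 30 overall (Protocol 14.3, SAP 6.0). The documents do not say how many dosed patients might lack a measurable lesion. I assume one for illustration; the expected case is none.

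**Largest possible shift.** Let n be the number treated and x the number of those with the event. One treated patient is excluded.

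- If the excluded patient had the event, the shift is x/n − (x−1)/(n−1) = (n−x)/[n(n−1)]. It is largest at x = 1, where it equals 1/n.
- If the excluded patient did not have it, the shift is x/(n−1) − x/n = x/[n(n−1)]. It is largest at x = n−1, where it again equals 1/n.

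| Group | Not replaced | Replaced |
|---|---|---|
| sALCL | 1/8 = 12.5 points | 1/9 = 11.1 points |
| HL | 1/22 = 4.5 points | 1/23 = 4.3 points |
| Overall | 1/30 = 3.3 points | 1/31 = 3.2 points |

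The maximum arises, for example, when the excluded patient is the only one with the event. In sALCL with replacement, 1/9 of treated patients (11.1%) would be tabulated as 0/8.

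**A more ordinary case.** Take an AE in half of the treated patients, including the excluded one, with no replacement. Overall, 15/30 (50.0%) would be tabulated as 14/29 (48.3%). In sALCL, 4/8 (50.0%) would be tabulated as 3/7 (42.9%).

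**Chance of seeing an AE at all.** With a true rate of 5%, the probability of at least one case is 1 − 0.95^n. Overall it falls from 78.5% (n = 30) to 77.4% (n = 29). In sALCL it falls from 33.7% (n = 8) to 30.2% (n = 7).

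**No such patient.** All these differences are zero.

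**The case against.** The strongest objection is that the situation should hardly ever arise. Criterion 4 makes measurable disease a condition of entry, the site assesses it, and no exemptions are allowed. Response is assessed by the investigator and there is no endpoint committee (Protocol 12.0), so the documents describe no second reader who would routinely overturn the site's baseline reading. This stands, and it is why the point is minor. It does not make the case impossible: the definition of a measurable lesion in Protocol 10.3.14 asks for accurate measurement in two perpendicular directions, which criterion 4 does not state, so a later check could disagree with the site.

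Second, little safety information would be lost. SAEs, deaths and AEs leading to discontinuation have their own listings (SAP 7.11.1.1, 7.11.1.3 and 7.11.1.4), and dosing, vital signs and ECOG status are listed as well. This also stands: the loss is one patient's count in the summary tables. A non-serious AE that does not stop treatment has no dedicated listing, however, and its incidence is summarized only in the set in question.

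Third, the SAP 7.1 sentence on including all available data is a general statement about data handling and defines no population, and the Protocol 14.1.7 wording may simply be shorthand for safety/mITT. Both are fair readings. Neither rescues the tables, because the specific rule in SAP 7.11 governs them. If SAP 7.1 expresses the intention, the definition in 7.2.1 does not carry it out.

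Fourth, the 12.5-point figure is a ceiling, and the figures with replacement assume that a patient without a measurable lesion would count as not response evaluable, which Protocol 10.6 does not say outright. Both limits are accepted.

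Finally, it can be said that only the safety and exposure tables need changing. But once the combined set is split, every section that names it must be assigned to one set or the other.

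**Conclusion.** The concern holds, as a minor defect in the definition of an analysis set. Under the current wording an exposed patient without a measurable baseline lesion would be left out of the safety incidence tables, and no other defined set would bring that patient back. The expected effect is nil. With one such patient, no tabulated incidence can move by more than 12.5 points in sALCL, 4.5 in HL or 3.3 overall, and an ordinary AE would usually move by less. These bounds rest on the planned group sizes and on the assumption of a single affected patient.

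**What to change.** Split the set in SAP 7.2.1:

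- *Safety population:* every patient who receives any amount of brentuximab vedotin, including a dosed patient who is later replaced.
- *mITT population:* members of the safety population with measurable lesions at Baseline.

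Reword the default-use sentence in 7.2.1 to match, and assign the sections as follows:

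- Safety population: 7.3 (disposition denominator), 7.4 (demographics and baseline disease), 7.6 (prior and concomitant medication), 7.7 (exposure) and 7.11 (safety).
- mITT population: wherever 7.8 and its subsections now name safety/mITT, and the B symptom resolution rate.
- Unchanged: the per-protocol, PK and Immunogenicity sets.

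Record the departure from Protocol 14.1.1 in SAP 7.13, as was done for the Immunogenicity population.

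The cost is wording in seven SAP sections (7.2.1, 7.3, 7.4, 7.6, 7.7, 7.8 and 7.11), one extra population flag and one entry in 7.13. The SAP would differ from Protocol 14.1.1 until the protocol is amended. Safety and baseline tables would have a different denominator from the efficacy tables only if a dosed patient lacks a measurable lesion. No new data are needed. Because mITT keeps the present conditions, ORR, sample size and power do not change.
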